1.2 Study Rationale

1.2.1 Dosimetry Group

The successful implementation of [⁶⁸Ga]Galmydar in humans could provide a new mechanism-driven tracer for PET MPI, and successful realization of aims could ultimately take PET MPI to underserved regions nationwide and developing countries worldwide, where an ¹⁸F-distribution business model would have limitations. [⁶⁸Ga]Galmydar PET MPI could enable quantification of myocardial flow reserve (MFR= stress MBF / rest MBF that carries important diagnostic and prognostic information) that may play an additional important role to evaluate or monitor the effectiveness of preventive medical care or the treatment response on the function of the heart vessels in CAD individuals. These benefits combined with the minimal risks weight the ratio in favor of moving the PET radiotracer [⁶⁸Ga]Galmydar into human subjects. This component of the study will determine the biodistribution and calculate the radiation dosimetry of [⁶⁸Ga]Galmydar in normal healthy volunteers. Our radiation dosimetry studies in mice [9] extrapolated to human dosimetry estimates using MIRD methodology suggest an allowable maximum injection dose of 8 mCi in humans. The maximum Effective Dose for one 8 mCi intravenous administration of [⁶⁸Ga]Galmydar and three whole-body CT scans with CT attenuation scans results in a gender average radiation dose of 2.84 rem that is well within 57% of the allowable annual dose for radiation workers.

1.2.2 Rest/stress Group

A rest/stress myocardial ¹³N-ammonia PET/CT is clinically indicated for the detection of flow-limiting, obstructive coronary artery disease (CAD). Myocardial perfusion PET provides images of a higher quality than SPECT, due to higher spatial and contrast resolution, higher scanner sensitivity, and accurate attenuation correction. In addition, the concurrent quantification of myocardial blood flow (MBF) affords the assessment of hyperemic MBF during pharmacologic vasodilation and at rest and, thus, the computation of the myocardial flow reserve (MFR= MBF stress/MBF rest). The concurrent assessment of hyperemic MBF and/or MFR aids in the identification and characterization of multi-vessel CAD, microvascular dysfunction, and prognostication.

We will compare the results of [⁶⁸Ga]Galmydar PET/CT MPI to the results of ¹³N-ammonia PET/CT MPI in a group of 20 symptomatic patients and 10 normal control subjects without symptomatology. Half of the symptomatic patients recruited will have a SPECT MPI study positive for ischemia in two myocardial segments with referral for invasive coronary angiography (ICA) as part of their routine standard-of-care (n=10), and half with normal SPECT MPI and no ICA referral (n=10). Patients referred for ICA will undergo their [⁶⁸Ga]Galmydar and ¹³N-ammonia PET/CT MPI studies prior to intervention. In addition, as a completely normal control, another 10 subjects without symptomatology or known cardiovascular disease will also undergo both ¹³N-ammonia PET/CT MPI and [⁶⁸Ga]Galmydar PET/CT MPI. In total 30 patients or normal human subjects will be studied.

1.3 Risks and Benefits

[⁶⁸Ga]Galmydar shows critical traits desirable in PET MPI. Additionally, despite the fact that concentrations of radiotracer needed for PET imaging are extremely low and rarely a concern, preclinical toxicity studies were conducted and thoroughly investigated according to FDA guidelines for new radiopharmaceuticals. The small animal toxicity report is located in the appendices of the initial IND submission.

In summary, a non-GLP 14-day single dose exploratory toxicity study of Galmydar was performed in male and female Sprague Dawley rats (study number, 2682-207370NI, Innotiv Maryland Heights, Missouri). The toxicity of Galmydar, a radiopharmaceutical diagnostic drug, was studied when administered as a single intravenous (IV) dose to male and female Sprague Dawley rats. Ten animals per sex from each group were euthanized for postmortem examination 24 hours after dose administration and 5 animals per sex from each group were euthanized for postmortem examination on Day 14 after administration.

Each treatment group (Group 1 and Group 2) was comprised of 15 male and 15 female Sprague Dawley rats. On Day 1, rats were administered either the vehicle control (Group 1) or 0.8 mg/kg Galmydar (Group 2) via IV injection at a dose volume of 1 mL/kg.

Physical examinations were conducted prior to randomization into groups. Clinical observations were recorded hourly at 1, 2, and 3 hours post-dose and once daily on Days 2–14. Body weights were measured prior to initiation of dosing on Day 1 and daily thereafter. Mortality observations were recorded once daily (PM observations). Blood samples for the evaluation of clinical chemistry and hematology endpoints were collected on Day 2 and Day 14 from both groups. Following blood sample collections, necropsy was conducted. Protocol-specified tissues were collected and evaluated grossly, select organs were weighed, and tissues were fixed for microscopic evaluation. A subset of fixed tissues were subsequently processed and evaluated microscopically.

Based on the absence of test article-related effects on body weight, clinical observations, clinical pathology or microscopic findings, a single IV administration of 0.8 mg/kg of Galmydar was well-tolerated in male and female Sprague Dawley Rats at both 24 hours (Day 2) and 14 days after dosing.

The findings above decrease the likelihood that human toxicity will be a hurdle. While information in humans is not yet available, our preliminary animal data shows high agreement in MPI performed with [⁶⁸Ga]Galmydar and ¹³N-ammonia. The success of this study of [⁶⁸Ga]Galmydar in human subjects could provide a mechanism-driven tracer for PET MPI, and ultimately take PET MPI to underserved regions nationwide and developing countries worldwide, wherein ¹⁸Fluorine distribution business models have limitations, with requirements for nearby cyclotron facilities. Overall, [⁶⁸Ga]Galmydar PET MPI could enable quantification of myocardial flow reserve that carries important diagnostic and prognostic information and that may play an important role in the

diagnosis of coronary artery disease and in the evaluation and monitoring of the effectiveness of treatment response. These benefits and minimal risks weight the ratio in favor of this hypothesis-driven diagnostic imaging research project.

2 STUDY OBJECTIVES

2.1 Primary Objective

The primary objective of the proposed study is to evaluate the potential of [⁶⁸Ga]Galmydar PET/CT MPI for the noninvasive detection of coronary artery disease. We will evaluate [⁶⁸Ga]Galmydar PET/CT MPI in comparison to ¹³N-ammonia PET/CT MPI to quantitatively assess myocardial blood flow (MBF) in patients with suspected or known coronary artery disease (CAD) undergoing clinical SPECT MPI. In addition, perfusion and MBF findings with [⁶⁸Ga]Galmydar will be compared to the results of coronary morphology or stenosis severity in those patients undergoing invasive coronary angiography (ICA) based on abnormal SPECT MPI. The performance of rest/stress [⁶⁸Ga]Galmydar PET/CT in comparison to ¹³N-ammonia PET/CT in normal subjects without cardiovascular disease will be performed as a control.

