8 IMAGE PROCESSING AND ANALYSIS

8.1 Rest Stress Group

8.1.1 PET Images

All images will be reconstructed at 5-min (a delay to allow for blood-pool clearance) using reconstruction matrix at 168 × 168 × 109, with a pixel size (2 × 2 × 2 mm). Scatter, decay, and random corrections will also be applied to the reconstructed images. Static myocardium perfusion and gated myocardial function images will be generated by skipping the first 5 minutes of the list mode data acquisition. Dynamic image sequence will be reconstructed for quantitative blood flow evaluation. Comparative quantitative blood flow will be evaluated with Carimas and also using QPET or 4DM software⁶⁵ available through our departmental image processing servers (MIM/Vista and Hermes). Myocardial image processing techniques will then be applied to the gated datasets. The myocardial wall segment analysis will be performed using the 17-segment American Heart Association model⁶⁶.

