9 STATISTICAL PLAN

Continuous variables will be expressed as mean (or median) and range or standard deviations. Categorical variables will be expressed as frequencies. The diagnostic efficacy of [⁶⁸Ga]Galmydar and ¹³N-ammonia PET MPI will be assessed following blinded and independent reads of PET MPI data using ICA as the truth standard. Analysis of diagnostic efficacy will be performed by the reader. The analysis of diagnostic certainty will be a modified majority rule in which the median rating will be used when three readers have 3 different ratings. Similarly, summaries and comparisons of Summed Stress Score (SSS), the Summed Rest Score (SRS), and the Summed Difference Score (SDS) measures will use the median of the results of 3 blinded readers. The sensitivity and specificity and corresponding 95% confidence interval of each radiotracer will be reported. Normalcy rate will be determined in the patients with a low likelihood of CAD and no ICA and be calculated as % of patients with normal/probably normal studies. Agreement for the diagnostic efficacy (presence/absence of CAD) between [⁶⁸Ga]Galmydar and ¹³N-ammonia PET MPI will be compared using a kappa statistic. The agreement between the quality of scan will be assessed using a weighted kappa and the SUV uptake will be assessed using an intra-class correlation coefficient. The ROC analysis will be performed using 17 segment model (according to the American Heart Association Guidelines) to assess the diagnostic efficacy in detection of obstructive coronary disease. The area under ROC and confidence intervals will use the empirical approach developed by DeLong, et al.⁶⁸ The inter-reader agreement between 3 blinded readers will be estimated by comparison of dichotomized ratings (normal/abnormal) and presented using kappa and percent agreement. Intra-reader agreement in each of the reader will be performed by randomizing 10% of the repeat images in the blinded read and will be estimated using kappa and percent agreement. All tests will be two-sided and a significance level of 5%.

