9.1 Sample size justification

While information in humans is not available, our preliminary animal data shows high agreement between [⁶⁸Ga]Galmydar and ¹³N-ammonia. Therefore, we expect to see strong agreement between the diagnostic efficacies of these two radiotracers in this sample of patients. A sample size of 20 patients results in a two-sided 95% confidence interval with a width of 0.26 (lower

limit=0.669, upper limit=0.931) assuming strong agreement between the radiotracers (a kappa of 0.8) and a standard deviation of 0.3. Sample size calculations were conducted in PASS v14.

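### Quantitative blood flow against 13N-ammonia is part of the primary objective, but the statistical plan has no analysis of it and no stated precision for it

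*Combined protocol and SAP*

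**What the plan says.** Section 2.1 has one primary objective with four parts. It opens with the tracer's potential "for the noninvasive detection of coronary artery disease". It then compares the two tracers "to quantitatively assess myocardial blood flow (MBF) in patients with suspected or known coronary artery disease (CAD) undergoing clinical SPECT MPI", sets Galmydar perfusion and MBF against angiographic stenosis in patients who go to invasive coronary angiography (ICA), and compares the tracers in normal controls.

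Section 9.1 sizes one quantity. The sponsor writes that "we expect to see strong agreement between the diagnostic efficacies of these two radiotracers in this sample of patients" and continues: "A sample size of 20 patients results in a two-sided 95% confidence interval with a width of 0.26". The inputs are a kappa of 0.8 and an SD of 0.3. Section 9 defines this agreement as kappa on presence or absence of CAD.

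Section 9 also lists sensitivity and specificity against ICA, normalcy rate, weighted kappa for image quality, an intraclass correlation for SUV, ROC area, the summed scores, and inter- and intra-reader agreement. It mentions neither MBF nor MFR, and it labels nothing as primary.

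MBF appears only in Section 8:
- Section 8.1.1: "Comparative quantitative blood flow will be evaluated with Carimas and also using QPET or 4DM software".
- Section 8.1.2: absolute regional MBF is to be reported.
- Section 8.1.4: Galmydar MBF is plotted against microsphere and ammonia MBF. The extraction parameters α and β are found by relating Galmydar K1 to those same references. Several versions of MFR (tracer-derived, retention-derived, SUV-derived) are compared with no statistic named.

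**The concern.** A quantity named in the primary objective should have an estimator, an analysis set and some statement of how precisely it will be known. MBF has none of these. The stated kappa precision cannot stand in for it: kappa uses only the readers' normal or abnormal calls, so a difference in absolute flow that leaves those calls unchanged leaves kappa unchanged.

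At stake is whether the trial can answer a question it poses. Sections 1.2.1 and 1.3 present flow-reserve quantification as a main benefit of the tracer. If the results hold only plots and summaries from two or more packages, the reader will have no agreement estimate with an interval. The version of MBF to emphasise would then be chosen after the data are seen.

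**Working it through.** **1. The plan's own figure.** Inputs from Section 9.1: kappa 0.8, SD 0.3, n = 20.

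0.8 ± 1.96 × 0.3/√20 = 0.8 ± 0.131 = 0.669 to 0.931, width 0.263.

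This reproduces the stated limits. The arithmetic is right; the issue here is what it covers. I take the SD of 0.3 as given.

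**2. Objective against analysis.**

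| Part of Section 2.1 | Statistic in Section 9 | Precision in Section 9.1 |
|---|---|---|
| CAD detection | Sensitivity, specificity, ROC area; tracer kappa on CAD presence | Kappa only |
| MBF against 13N-ammonia | None | None |
| Perfusion and MBF against ICA | Perfusion reads: sensitivity, specificity, ROC area. MBF: none | None |
| Normal controls | No tracer comparison named for this group | None |

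The only agreement statistic in Section 9 for a continuous uptake measure is the intraclass correlation, and it is for SUV, not MBF.

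**3. What would have to be settled for MBF.** Sections 8.1.1 to 8.1.4 leave open rest, stress or MFR; which MFR version; Carimas, QPET or 4DM; and regional values (8.1.2) or left-ventricular means (8.1.4). No main choice is named.

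**4. Precision available with n = 20.** The documents give no SD for paired MBF differences, so I assume a range. Let d be the Galmydar-minus-ammonia difference as a percentage of the ammonia value, in the 20 symptomatic patients of Section 4.1.

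Half-width of the 95% CI for the mean of d = t(0.975, 19) × SD/√20 = 2.093 × SD/4.472 = 0.468 × SD.

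Approximate half-width for each limit of agreement = 2.093 × SD × √(1/20 + 1.96²/(2 × 19)) = 2.093 × 0.389 × SD = 0.814 × SD.

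| Assumed paired SD | Mean difference, ± | Each limit of agreement, ± |
|---|---|---|
| 15% | 7% | 12% |
| 25% | 12% | 20% |
| 35% | 16% | 28% |

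In absolute units, assumed SDs of 0.3, 0.5 and 0.7 mL/min/g give ± 0.14, 0.23 and 0.33 for the mean difference.

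**5. Calibration.** Section 8.1.4 models K1 as extraction fraction times MBF and chooses α and β by relating Galmydar K1 to ammonia MBF, among other references. If that fit uses the same patients, the fitted curve runs through the middle of their ammonia values. The mean Galmydar-minus-ammonia difference is then close to zero largely by construction, and disagreement shows mainly as scatter. The section does not say which sample supplies the fit. It mentions microspheres and an animal model as well as ammonia.

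**The case against.** The strongest reply is that the sized statistic does serve the objective. The lead sentence of Section 2.1 is detection of CAD, and kappa on presence or absence of CAD bears directly on it. This stands. A reader might infer that MBF alone is the primary objective and that the trial was sized on something unrelated; the section does not support that.

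The study is also a single-center phase 0/1 imaging study with precision-based sizing and a feasibility purpose. Absence of a power calculation or a formal testing hierarchy is not an error here. That stands too, but it does not excuse leaving one named part of the objective without an estimate.

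A reader might go further and expect kappa and MBF to give opposite answers, for instance a high kappa while Galmydar reads stress flow well below ammonia. In principle they can diverge. A figure for how often would come from assuming that the calls are independent of flow, and it would ignore the calibration in Section 8.1.4, which may remove most of a mean shift. The documents do not support such a figure.

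A reader might also see an inflated false-positive rate in "All tests will be two-sided and a significance level of 5" per cent. Section 9 consists mostly of estimates, and the sponsor expects agreement, so a chance difference between tracers would count against it. Family-wise error does not measure the risk of selectively claiming agreement.

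**Conclusion.** The point holds as a gap in the plan. One explicit part of a composite primary objective, quantitative MBF against 13N-ammonia, has no estimator, no main software package and no stated precision. The kappa interval of 0.669 to 0.931 says nothing about it. No statistic is named as the primary result.

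The attainable precision is modest but usable: about ± 7% to ± 16% for the mean difference with 20 complete pairs, resting on assumed paired SDs of 15% to 35%. Those figures are meaningful only if α and β are not fitted in the patients being compared. The missing MBF analysis follows from the text alone and needs no assumption.

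**What to change.** In Section 9, add a paired Galmydar-minus-ammonia MBF agreement analysis. One suitable form is stress MBF in the 20 symptomatic patients, reported as mean difference with 95% CI and limits of agreement. Name one software package for the main analysis and make the others sensitivity analyses. State whether values are regional or left-ventricular means.

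In Section 8.1.4, require that α and β come from data outside the compared patients or from cross-validation. The 10 controls, who have both tracers, are one possible source.

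In Section 9.1, keep the kappa statement and add the expected MBF precision with its assumed SD.

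State whether CAD kappa or MBF agreement is the primary result and label the rest secondary or exploratory. Either choice is compatible with Section 2.1, and it is the sponsor's to make.

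The cost is wording in Sections 8.1.4, 9 and 9.1, and a little more analysis work, with no new patients or scans. The drawback is that the stated MBF precision will look modest.

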2.2 Secondary Objectives

To evaluate dosimetry, biodistribution, and safety, and imaging characteristics following a single [⁶⁸Ga]Galmydar injection in normal healthy volunteers at rest.

3 STATEMENT OF INVESTIGATOR

[name], the Sponsor-Investigator of the IND, [name]., Principal Investigator, and [name]., Authorized User will comply with the state and federal regulations related to the conduct of all clinical investigations with the administration of [⁶⁸Ga]Galmydar. A Form FDA 1572 is included with the IND application.

The study protocol will not be initiated before receiving all required regulatory approvals obtained from the Institutional Review Board (IRB)/Human Research Protection Office (HRPO), the Radioactive Drug Research Committee (RDRC), and receipt of the study activation letter from the Food and Drug Administration (FDA).

4 STUDY DESIGN AND METHODS

A single center, phase 0/1 clinical imaging study designed to assess the role of [⁶⁸Ga]Galmydar PET/CT imaging in human subjects.

4.1 Study Population

We will recruit up to 38 participants for the dosimetry and rest/stress groups. Healthy adult normal volunteers (n=8, 4 males; 4 females) for whole-body imaging (dosimetry group) and patients who had a prior clinical SPECT MPI examination that is positive or negative for ischemia.

Thirty (30) subjects will be enrolled in the rest/stress group. Symptomatic patients (n=20) will have undergone a SPECT MPI examination. Ten patients in this group will have had a study positive for ischemia in two myocardial segments and referred for invasive coronary angiography (ICA) as part of their routine standard-of-care. [⁶⁸Ga]Galmydar PET imaging will occur prior to intervention. The other ten patients will have a normal SPECT MPI and no ICA referral. Subjects (n=10) who are asymptomatic and without history of cardiovascular disease will serve as a normal controls.

4.2 Inclusion and Exclusion Criteria

In order for participants to be eligible for study enrollment, an individual must meet the inclusion criteria. An individual who meets any of the exclusion criteria will be excluded from participation in the study.

4.2.1 Dosimetry Group

Healthy adult normal volunteers will be enrolled in the dosimetry group.

4.2.1.1 Inclusion criteria

- Healthy men and women, 18–99 years of age and any race;

4.2.1.2 Exclusion criteria

- Inability to receive and sign informed consent;
- Positive urine screen for drugs of abuse at screening or before dosing or over-the-counter drug use or herbal preparations within the 2-week period prior to enrollment;
- Participation in another research study with a study drug, including a diagnostic or therapeutic radiopharmaceutical, to be administered during this study or which was or will be administered within 10 half-lives of the radiopharmaceutical.
- Severe claustrophobia;
- Pregnant or breastfeeding.
- Body mass index < 18 kg/m² or > 40 kg/m².

4.2.2 Rest/Stress Group

Twenty symptomatic patients will have undergone a SPECT MPI examination. Ten of these patients will have had a study positive for ischemia in two myocardial segments and referred for invasive coronary angiography (ICA) as part of their routine standard-of-care. [⁶⁸Ga]Galmydar PET imaging will occur prior to intervention. The other ten patients will have had a negative for ischemia SPECT MPI and no ICA referral. Ten healthy adult normal volunteers, who are asymptomatic, without history of cardiovascular disease or significant cardiovascular risk factors, will serve as control subjects.

Asymptomatic normal controls and symptomatic patients who have undergone a SPECT MPI examination that is normal or positive and prior to ICA intervention, will undergo a rest/stress [⁶⁸Ga]Galmydar PET MPI and rest/stress ¹³N-ammonia PET MPI with a minimum of a 3-day separation.

4.2.2.1 Inclusion Criteria

- Male and female, 18-99 years of age and any race;
- Have had a prior clinical SPECT MPI positive for ischemia in two myocardial segments and referred for invasive coronary angiography (ICA) or have had a prior clinical SPECT MPI negative for ischemia;

4.2.2.2 Exclusion Criteria

- Inability to receive and sign informed consent;
- Percutaneous coronary intervention (PCI) or coronary artery bypass grafting (CABG) within 6-months prior to SPECT or in the intervening days between SPECT and PET examination;
- Participants who have received chemotherapeutic agents within 6 months of enrollment;
- Heart failure (left ventricular ejection fraction $\leq 35\%$);
- Known non-ischemic cardiomyopathy;
- Inability to undergo pharmacologic stress testing with regadenoson (Lexiscan). Contraindications include:
 - Symptomatic bradycardia or second to third degree atrioventricular (AV) block;
 - Pre-existing obstructive lung disease with active wheezing, i.e., COPD, asthma with active wheezing that precludes the safe administration of the pharmacological stress agent according to the approved label;
 - Uncontrolled and severe hypertension (e.g. systolic blood pressure >200 mmHg, diastolic blood pressure >110 mmHg);
 - Baseline hypotension (e.g. systolic blood pressure < 90 mmHg, diastolic blood pressure <50 mmHg);
- Women who are pregnant or breastfeeding;
- Severe claustrophobia;
- Weight ≥ 500 lbs (weight limit of PET/CT table)

- Administration of any diagnostic or therapeutic radiopharmaceutical, not part of this study, within a period either prior to or after equal to 10 half-lives of the radiopharmaceutical.
- Any condition that in the opinion of the Principal Investigator or designee could increase risk to the participant, limit the participant's ability to tolerate the research procedures or interfere with collection of the data such as:
 - Inability to lie still or unable to tolerate a supine position with arms up over the head for up to a 60-minute PET scan due to chronic back/shoulder pain or arthritis as assessed by physical examination and/or medical history;
 - Current or past history of major medical illness, i.e., severe kidney or liver problems;
 - Patients who suffer an intervening clinical event such as worsening angina pectoris or myocardial infarction or whom undergo a myocardial revascularization procedure or have myocardial ischemia at rest;

